7.1.2 Psychiatric History

Descriptive statistics (N, mean, SD, median, and range) of baseline disease characteristics will be provided by treatment group, and overall for both the ITT and PP populations for

- Age at the first onset of initial symptoms of BED (years);
- Duration of initial onset of initial symptoms of BED to screening (in years);
- Age at the first onset of initial diagnosis of BED (years);
- Duration of initial onset of initial diagnosis of BED to screening (in years);
- the average number of binge eating days per week in the preceding six months
- the least number of binge eating days per week in the preceding six months
- the maximum number of binge eating days per week in the preceding six months
- the average number of binge episodes per week in the preceding six months

Frequency distribution of the following variables will be summarized by treatment

- the least number of binge eating days per week in the preceding six months
- the maximum number of binge eating days per week in the preceding six months

The number and percentage of subjects in each of the following categories (and sub-categories) at baseline will also be summarized by treatment group

- the average number of binge eating days per week in the preceding six months: 2 to <3, 3 to <4, 4 to <5, 5 to <6, and 6 to 7;
- the average number of binge episodes per week in the preceding six months: 2 to <4, ≥ 4 to ≤ 7 , >7 to <14, and ≥ 14 .

Summaries of any other current psychiatric disorders present at screening include DSM-V codes for the ITT and PP populations. If a subject had 1 or more history events more than once, the subject will be counted only once under any given DSM-V code.

7.1.2.1 Psychiatric Family History

The number and percentage of subjects whose biological relatives (mother, father, siblings, children, extended family) have/had each of pre-specified psychiatric history will be summarized by treatment group for both the ITT and PP populations.

Listings of psychiatric history and psychiatric family history are provided for all randomized subjects.

7.1.3 Disposition Information

Subject disposition for all randomized subjects will be summarized by treatment group using the following categories:

- Subjects who are randomized;
- Subjects who are randomized, but not dosed;
- Subjects in the ITT population;
- Subjects in the Safety population;
- Subjects in the PP population;
- Subjects in the ITT who complete the Week 12 visit;
- Subjects in the ITT who complete the Week 12 visit and enter into the open-label extension study;
- Subjects who discontinue during the DB period.

- Subjects in the withdrawal population;
- Subjects who complete the withdrawal period;
- Subjects who discontinue during the withdrawal period

For subjects who discontinue from the study after randomization, the corresponding reasons for discontinuation will be summarized for DB period and withdrawal period, respectively. For subjects who are excluded from the PP population, the corresponding reasons will be summarized by treatment.

For subjects who consented but were not randomized (eg, screen failures) the corresponding reasons for discontinuation will be summarized.

Kaplan-Meier plot of the time to early discontinuation in the DB period will be presented by treatment group. Subjects who complete 12-weeks DB treatment period will have their time to treatment discontinuation censored on the study day of end of the treatment period.

7.1.4 Treatment Compliance

At each post-baseline (Weeks 1 – 12) visit, prior to dispensing study medication, previously dispensed study medication will be retrieved and assessed by tablet count.

Unless otherwise specified, compliance in the double-blind phase will be calculated for each post-baseline visit and overall as follows:

- Percent compliance = (number of tablets taken / number of tablets should have taken) x 100.
- Number of tablets taken = number of tablets dispensed – number of tablets returned.
- Number of tablets should have taken = (number of tablets supposed to take in a day) x (number of exposure days).
- Number of exposure days = last dose date – first dose date + 1.

For each post-baseline visit, if medication kit usage information is incomplete (ie, meet one of following conditions: any dispensed medication kit at the visit has missing number of tables returned, or has missing dosing start or ending date), the corresponding compliance will not be derived and will be set as missing.

For an assessment period that involves multiple study visits (ie, overall double-blind treatment period), if at some visit(s) the drug usage information is incomplete, then the other visits with complete information of kit usage will be used to derive the compliance rate. Number and percentage of subjects with incomplete medicate kit usage information will be summarized by study visit and treatment group.

Non-compliance is defined as less than 75% or more than 125% non-missing compliance with the study medication. Subjects with missing compliance will not be classified as non-compliant.

Descriptive summary statistics (N, mean, median, and range) will be provided by treatment group and overall for percent compliance. In addition, the number and percentage of subjects in the categories of the following variables will also be summarized by treatment group through the Week 12 visit:

- Compliant;
- Non-compliant (<75% or >125%);
- Non-compliant: <75%;
- Non-complaint: >125%;
- Complete and Incomplete medication kit usage information: complete, incomplete for 1-2 weeks, 3-4 weeks, and > 4 weeks visit period.

7.1.5 Extent of Exposure

Treatment duration is defined as the amount of elapsed time between the first and the last day that study medication was taken (inclusive). It will be calculated (in days) in terms of the difference in relative study days between the last and first dose of study medication, plus one

321

day. See [Section 6.1.9.2](#) for imputation rule if the end date of the medication intake is unknown or ‘confirmed’.

Descriptive statistics (N, mean, standard deviation, median, and range) will be presented by treatment group for treatment duration. Number of subjects with duration in each of following categories: ≥ 7 , ≥ 14 , ≥ 21 , ≥ 28 , ≥ 42 , ≥ 56 , ≥ 70 , and ≥ 83 days; 1-6, 7-13, 14-20, 21-27, 28-41, 42-55, 56-69, 70-82, and ≥ 83 days will also be presented by treatment group and overall. Return of the blister card at any given visit will not be a prerequisite for inclusion in exposure summary statistics if corresponding dose start and end dates are reported.

Note that exposure will be shown only up through the Week 12 visit or, for subjects with premature discontinuation, the last day of dosing of double-blind study drug for the subject.

7.1.6 Protocol Deviations

Deviations from the protocol, as adjudicated by Medical Monitor review, may have an impact on the efficacy analysis.

Protocol deviations that may impact on efficacy analysis include, but will not be limited to the following:

- Subject received any incorrect study treatment or was not dosed in DB period
- Overall missing diary rate in double-blind treatment period is $> 5\%$
- Subject does not have a baseline efficacy measurement or at least one post-baseline efficacy measurement for primary efficacy variable
- Subject was unblinded during the double-blind treatment period
- Subject does not have 28 days or more of exposure
- Subject that does NOT belong to one of the following 2 cases:
 - Case 1: there is no medication kit usage with incomplete information, and overall medication compliance is between 75% and 125%;
 - Case 2: if there is 1 or 2 medication kits with incomplete usage information, overall medication compliance per the worst case imputation is between 75% and 125%,
- Subject violated inclusion/exclusion criteria which have any potential impact on efficacy results
- Subject took >1 dose of a prohibited medication or more than one day of a prohibited dose of an allowed medication or received prohibited psychotherapy during the double-blind treatment period, that were judged to have a potential impact on the primary efficacy analysis based upon blinded medical review.

- If the subject tests positive for substance of abuse at any post-baseline visit during the double-blind period (through 10 days after the Early Termination Visit for subjects who discontinue prematurely or for subjects who complete the study but do not continue into the extension study; and, through the Week 12 Visit date for subjects continuing into the extension study), without a verified prescription for use of a drug that could have caused a positive test result (confirmed by medical review)

A complete list of subjects who met with at least one of above protocol deviation criteria, will be identified prior to database lock.

Subjects in ITT population regarded as protocol deviators per above criteria will not be included in the PP population. A summary of all these protocol deviations will be presented by treatment group and overall for all randomized subjects. Subjects will be counted once within each deviation category, regardless of how many deviations they have in that category. A listing of protocol deviations will be provided for all randomized subjects. A listing will also be provided for subjects who take any incorrect study drug.

In addition, regardless of potential efficacy impact, protocol deviations are collected during monitoring visits. Protocol deviations will be placed into the following categories: concomitant medications, dosing, enrollment criteria, laboratory, non-compliance, visit schedule, visit/procedure requirement, and other. Each instance of a protocol deviation will be reviewed and determined to be major or minor prior to database lock of the study.

Number and percentage of subjects with at least one major protocol deviation of each deviation category will be summarized by treatment group. A listing that presents all protocol deviations will be also provided.

7.1.7 Study Medication and Prior and Concomitant Medications

7.1.7.1 Prior and Concomitant Medications

Prior (ie, medications taken before initiation) and concomitant medications (ie, medications taken on or after initiation of double-blind study medication that were either started prior or after initiation of double-blind study medication) will be coded using World Health Organization (WHO) Drug Dictionary and Anatomical Therapeutic Chemical (ATC) codes.

Number and percentage of subjects taking prior and concomitant medications will be provided by level 3 ATC classification and preferred name by treatment group and overall. Since medications are coded to ATC classification by indication, preferred names may appear under multiple ATC classifications. Medications started after last dose of study drug will be included in the prior and concomitant medication listing only.

321

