10.3.3. Permitted Medications

The following medications are permitted during the study, with the restrictions noted:

- Sleep aids should be administered no more than once nightly and should not be used in combination. Concomitant use of lorazepam, temazepam, eszopiclone, zaleplon, zolpidem, zolpidem controlled release (CR), and melatonin is permitted at the discretion of the Investigator with the following restrictions:
 - Lorazepam (or equivalent benzodiazepine) is a permitted hypnotic up to a maximum daily dose of 2 mg/day
 - Temazepam (≤ 30 mg/day), eszopiclone (≤ 3 mg/day), zaleplon (≤ 20 mg/day), zolpidem (≤ 10 mg/day for males; ≤ 5 mg/day for females), zolpidem CR (≤ 12.5 mg/day for males; ≤ 6.25 mg/day for females), and melatonin (≤ 5 mg/day) may be administered at bedtime for insomnia, as needed
 - Use of any other sleep aids should be approved by the Medical Monitor
- Opiates may be allowed in rare cases for a limited period of time with prior authorization from the Medical Monitor
- Contraceptives

The date and time of the last dose taken prior to scheduled efficacy assessments of any sleep aid listed above must be recorded at each visit.

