11.8.10. Three-week Study Medication Withdrawal Period

In addition to during in-clinic visits, the CSSA and DESS will be completed during the 3-week study medication withdrawal period on non-clinic visit days. Clinical site staff will call the subject every other day during the study medication withdrawal period, beginning the second day after the last dose of study drug, unless a clinic visit is scheduled for that day (up to 3 times per day if the clinical site staff are unable to contact the subject on the first 2 attempts). Clinical site staff will record the responses to the CSSA and DESS in the subject's source information and in the CRF with the contact date and time. During these calls, clinical site staff will also assess and record AE(s) and concomitant medications.

A window of ± 1 day will be allowed for each weekly clinic visit and telephone call. If the subject cannot be contacted on a given day, during the next contact the study site staff will retrospectively collect the missed CSSA and DESS, in addition to the current day's CSSA and DESS.

11.8.10.1. Week 13 (Day 91 [± 1 day]¹): Visit 11

The following study related procedures will be performed:

¹ For early terminating subjects 7 days post last dose ± 1 day

- Record concomitant medications
- Collect vital signs and weight
- Perform ECG
- Record AEs
- Clinician review of binge eating diary and retraining, as necessary
- Administer scales:
 - MADRS (with SIGMA)
 - C-SSRS
 - HAM-A (with SIGH-A)
 - CSSA
 - DESS
- Collect sample for UDS
- Perform breath alcohol test

Subjects will complete the daily binge eating diary each day until the next clinic visit.

11.8.10.2. Week 14 (Day 98 [\pm 1 day]²): Visit 12

The following study related procedures will be performed:

- Record concomitant medications
- Collect vital signs and weight
- Perform ECG
- Record AEs
- Clinician review of binge eating diary and retraining, as necessary
- Administer scales:
 - MADRS (with SIGMA)
 - C-SSRS
 - HAM-A (with SIGH-A)
 - CSSA
 - DESS

² For early terminating subjects 14 days post last dose \pm 1 day

- Collect sample for UDS
- Perform breath alcohol test
- Remind subject to fast for at least 8 hours (water only) prior to Visit 13.

Subjects will complete the daily binge eating diary each day until the next clinic visit.

11.8.10.3. Week 15 (Day 105 [\pm 1 day]³) Visit 13

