15.4.2.8. Prior and Concomitant Medications

All medications will be coded using the World Health Organization drug dictionary (WHO-DD).

The prior medications will include medications taken before initiation and stopped prior to initiation of double-blind study medication. The concomitant medications will include medications taken after initiation of double-blind study medication that were either started prior to or after initiation of double-blind study medication.

The number and percentage of subjects taking prior and concomitant medication will be summarized by anatomical therapeutic chemical (ATC) classification and preferred name by treatment group.

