During the study and prior to database lock, the treatment assignments for all subjects are provided to the Bioanalytical Contract Research Organization (CRO) to facilitate plasma PK sample handling and analysis. No PK samples are analyzed for placebo subjects.

Protocol and IRT Amendment for Stratification Factor of Region

For this US study, there is no concern of ‘region’ difference for treatment effect. Sponsor’s initial intention of including stratification factor of region was to provide an optimization approach to ensure a balanced treatment assignment within each region. It should be noted that stratification by region was not implemented in study SEP360-221, which is also a US study with a similar study design.

The study team noticed on July 20, 2017 that the stratification by region was not implemented as planned, ie, the initiated sites in IRT were linked to incorrect regions (See [Section 6.1.5.1](#) for details). As of July 20, 2017, among 50 planned sites of this study, a total of 44 sites were screening subjects; and 137 subjects from 35 sites had already been randomized. Due to the ‘random’ nature of the incorrect assignment of region according to the root cause of this incident, the study team decided to remove stratification criteria related to ‘region’ to minimize the impact of this mistake. Stratification criteria were amended in study protocol V3.00 and randomization is to be balanced using only permuted blocks with baseline number of binge eating days per

321

week (3 – 4 binge eating days per week, > 4 binge eating days per week).

4. Changes in Planned Analyses

There is not any change made in this SAP from the analyses planned in the protocol.

5. Efficacy and Safety Variables

[Section 6.1.2](#) provides definitions of DB Baseline and Withdrawal Baseline. For the sake of simplicity, hereafter, Baseline and DB Baseline will be used in an interchangeable way.

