6.1.11.4.2 Start/End Dates for Prior/Concomitant Medication

Partial dates of non-study medication start/end date need to be imputed in order to classify the medications as prior or concomitant medications, or post-treatment medication (ie, medication initiated after the last dose of study medication). A conservative approach will be used to handle the incomplete date(s) for medication start/end date (ie, if the available incomplete date(s) cannot determine the concomitant relationship relative to the double-blind phase, the medication is considered as a concomitant medication).

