7.4.6 Assessments of Withdrawal Effects (CSSA, DESS, HAM-A, and MADRS)

CSSA total score, DESS total score, MADRS total score, and HAM-A total score will be summarized by presenting descriptive statistics (N, mean, median, and range) of observed values and change from withdrawal baseline by treatment and visit (ie, both clinic and non-clinic visits) for the withdrawal period.

A similar analysis will be performed by gender as well.

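### The SAP moves medications started after the last dose to a listing, an undeclared departure from the protocol, so new sleep-aid and benzodiazepine starts in the withdrawal period are not counted by arm

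*SAP*

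**What the plan says.** SAP 7.1.7.1 defines concomitant medications as those taken on or after the first double-blind dose, whenever they began. It plans counts and percentages by level 3 ATC class and preferred name, by treatment group and overall. It then makes one exception: "Medications started after last dose of study drug will be included in the prior and concomitant medication listing only".

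Protocol 15.4.2.8 plans the same kind of table by treatment group without that exception. Its definition covers "medications taken after initiation of double-blind study medication that were either started prior to or after initiation of double-blind study medication" and does not stop at the last dose. SAP section 4, Changes in Planned Analyses, reads: "There is not any change made in this SAP from the analyses planned in the protocol".

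The data exist. Protocol 10.3 records each medication with dose, start date, stop date and indication from Screening to Week 15. Protocol 11.8.10 adds, for the telephone contacts after the last dose: "During these calls, clinical site staff will also assess and record AE(s) and concomitant medications". SAP 6.1.11.4.2 already sorts medications into prior, concomitant, "or post-treatment medication (ie, medication initiated after the last dose of study medication").

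Sleep aids are allowed during the study under restrictions. Protocol 10.3.3 states: "Lorazepam (or equivalent benzodiazepine) is a permitted hypnotic up to a maximum daily dose of 2 mg/day", and it also allows temazepam, eszopiclone, zaleplon, zolpidem and melatonin. SAP 7.4.6 summarizes the CSSA, DESS, MADRS and HAM-A total scores in the withdrawal period as "observed values and change from withdrawal baseline by treatment and visit", with no reference to medication use.

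**The concern.** Assessing withdrawal effects after abrupt discontinuation is a stated secondary objective (Protocol 5.3, SAP 2.3). A new sleep aid or benzodiazepine begun in those three weeks matters to that objective in two ways. It may itself be a response to withdrawal symptoms, and it may act on items that the scales score. The CSSA covers anxiety, irritability and sleep disturbance. The HAM-A covers tension and insomnia. The MADRS covers inner tension and reduced sleep. A reader of the SAP 7.4.6 tables would want to know whether new starts were more frequent in one arm than in another, and the SAP gives no count. Because section 4 declares no change, a reader who relies on the protocol would also assume that these medications are in the by-arm table.

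**Working it through.** No figure in the plan needs reproducing. The check is a comparison of texts, followed by a short calculation that bears only on the choice of remedy.

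**1. One medication under both rules.** Take a sleep aid first used after the last dose.
- Protocol 15.4.2.8: taken after initiation, therefore concomitant, therefore counted by ATC class, preferred name and arm.
- SAP 7.1.7.1: started after the last dose, therefore in the listing and in no count.
- SAP 6.1.11.4.2: falls in the post-treatment class, to which no table is assigned.

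The rules give different tables, and SAP section 4 does not say so.

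**2. Is it counted by arm anywhere else?**
- Subject listings are generally sorted by randomized group (SAP section 7), so the records are visible by arm but not counted.
- The urine drug screen panel includes benzodiazepines and is collected at Weeks 13 to 15 (Protocol Table 2 and Appendix II). Its summary is specified under the treatment period (SAP 7.4.3.1), and it would show neither the drug nor its start date.
- Major protocol deviations are tabulated by category and arm (SAP 7.1.6). The categories are not specific to a drug or a period, and permitted sleep aids are not deviations.
- Sleep aids begun before the last dose and continued stay in the by-arm table. The gap therefore concerns new starts only.

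**3. What is still shown by arm?**
- Discontinuation-emergent adverse events, by system organ class and preferred term, and again for 1-7, 8-14 and 15 or more days of withdrawal (SAP 7.4.2).
- Events subject to additional monitoring, summarized separately for the withdrawal population (SAP 7.4.8.3.2). The protocol's sample list includes insomnia, anxiety, irritability, agitation and restlessness.
- CSSA and DESS, scheduled every other day from the second day after the last dose (SAP 5.2.2), windowed in two-day bins (SAP 6.1.4.2) and summarized for clinic and non-clinic visits (SAP 7.4.6).

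**4. Can the masking be sized?** Not from the documents. For illustration only, let *s* be the share of an arm with symptoms, all with the same score rise, let *f* be the fraction of those who start a sedative, and suppose that the sedative removes half of their rise. All three inputs are assumed.
- Planned summary, all assessments kept: fraction of the true mean rise shown = 1 − 0.5*f*. With *f* = 0.2 this is 0.90; with *f* = 0.4 it is 0.80.

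**5. Would dropping assessments made after a new start help?** Under the same model the mean is then taken over the 1 − *sf* who remain:
- fraction shown = (1 − *f*)/(1 − *sf*).
- With *s* = 0.3, *f* = 0.2: 0.8/0.94 = 0.85, against 0.90 as planned.
- With *s* = 0.3, *f* = 0.4: 0.6/0.88 = 0.68, against 0.80 as planned.
- Exclusion understates more whenever *s* < 0.5/(1 − 0.5*f*), which is 0.5/0.9 = 0.56 for *f* = 0.2 and 0.5/0.8 = 0.63 for *f* = 0.4.

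Exclusion removes the symptomatic subjects, so unless more than about 56-63% of the arm is symptomatic it makes the summary more reassuring, not less.

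**The case against.** The strongest defence is that a medication begun after the last dose is not concomitant with study drug in the ordinary sense, so the SAP only clarifies. The protocol's own usage goes against this. It sets no end at the last dose in 15.4.2.8, records medication to Week 15 under its heading for concomitant medications in 10.3, and uses that same term for what is recorded at the withdrawal-period calls in 11.8.10. If the SAP means something narrower, that is a change and should be declared.

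The second defence is that the evidence of withdrawal is not lost, and most of this stands. A sedative does not erase the adverse event that prompted it. That event is tabulated by arm and by withdrawal interval, and the frequent CSSA and DESS contacts may capture symptoms before a sedative is started. Benzodiazepines are permitted only for sleep (Protocol 10.3.1 and 10.3.3), so the permitted route is narrow. These tables count reported symptoms, however. They do not show who was medicated or which later ratings followed a new start.

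The third defence is that following Protocol 15.4.2.8 literally would pool post-dose starts with twelve weeks of treatment-period use. That is right. The protocol does not ask for a separate withdrawal-period table, so restoring its wording alone would not show the comparison that is useful here.

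**Conclusion.** The point stands as an undeclared difference between protocol and SAP that leaves a small but relevant gap: new sleep-aid or benzodiazepine starts after the last dose are not counted by arm in any planned output. It affects the reading of descriptive summaries for a secondary safety objective. It does not touch the efficacy analyses or the type I error control.

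A reader might infer more, namely that the analysis could report no withdrawal effect while the contrary evidence is tabulated nowhere. The documents do not support that. The adverse-event and additional-monitoring tables by arm would show the prompting symptoms, and the listing holds the medication records. That such use can lower the scores is itself an inference from scale content and permitted use, not something the documents state. The 0.80-0.90 range in the working rests entirely on assumed inputs and should not be cited as an estimate of bias.

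**What to change.** - **SAP 7.1.7.1:** replace the listing-only rule with a table, by treatment group in the withdrawal population, of the number and percentage of subjects starting each post-treatment medication (the class defined in SAP 6.1.11.4.2). Add one combined row for any sedative, hypnotic or benzodiazepine newly started. Keep the listing.
- **Reading the table:** set it beside the SAP 7.4.6 summaries and the discontinuation-emergent adverse event tables. SAP 7.4.1 assigns the modified withdrawal population to adverse events, CSSA and DESS, so state the denominator in a footnote.
- **SAP section 4:** declare the difference from Protocol 15.4.2.8.
- **Do not add** repeat CSSA, DESS, HAM-A or MADRS summaries that exclude assessments after a new start, for the reason shown in the working.

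The cost is a few lines of SAP text and one descriptive table from data already recorded at visits and calls through Week 15. No procedure or treatment rule changes.
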